4. OBJECTIVES AND OUTCOME MEASURES

Objectives	Outcome Measures	
Primary objective		
To describe the frequency of LUS abnormalities consistent with pulmonary oedema	Frequency endpoint: proportion of patients with LUS consistent with pulmonary edema Severity endpoint: LUS aeration score (numerical 0 to 36)	
To describe the timing and entity of edema resolution after delivery	Frequency endpoint: Fraction of patients with improvement or resolution of LUS findings. Quantitative endpoint: delta LUS score between T1 and T2	
Secondary objectives: To describe the frequency of acute respiratory failure in patients with Severe Pre- eclampsia and in patients with Eclampsia	Proportion of patients with acute respiratory failure (see definition)	
Frequency of other LUS findings	 Proportion of patients with: consolidations isolated pleural effusion minor LUS findings Calculation of the LUS ARDS score 	
Frequency of organ support strategies	Fraction of patients that receive: - oxygen - CPAP - Mechanical ventilation	
Frequency of patients with abnormal cardiac function	Defined as either low cardiac output measured by ultrasound	
Oxygenation assessment	SpO ₂ to FiO ₂ ratio	
Frequency of Major Direct Obstetric Complications	Fraction of patients with at least one additional MDOC (APH, PPH, sepsis, uterine rupture, obstructed labour)	
Frequency of Indirect Obstetric complications	Fraction of patients with at least one among stroke, severe malaria, acute kidney injury and cardiac insufficiency	
Frequency of perinatal complications	IUFD, Apgar score, Admission to special care baby unit (SCBU)	

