5. STUDY DESIGN

This will be a single centre, prospective, cohort study of patients with severe pre-eclampsia and eclampsia. The expected duration of study is 1 year. All patients with suspected severe pre-eclampsia or eclampsia will undergo screening upon admission to HDU and the Eclamptic ward. Eligible patients will undergo a systematic clinical and LUS examination, straight after admission (**before delivery**). Clinical examination will focus on signs of respiratory, neurologic and cardiac failure. Lung ultrasound will be performed using a MyLab[™]Five ultrasound machine (Esaote Spa, Genova, Italy) and a low frequency (2.5–5 MHz) convex probe or a Butterfly ultrasound probe (Butterfly, USA). Lung ultrasound will be performed using the

validated 12-region method, evaluating 2 anterior regions, 2 lateral regions and 2 posterior in each hemithorax (18,28,29). As heart failure is a common finding in preeclamptic women, echocardiography performed with a cardiac sector probe, will enable real-time assessment of maternal cardiac contractility and cardiac output. The same clinical, LUS and echocardiographic assessment will be repeated between 24 h to 72 h (after delivery). Whenever the pre-delivery timepoint is not feasible due to late arrival, emergency scenario or postpartum onset, the after delivery examination only will be performed.

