8. INVESTIGATIONS

8.1. Ultrasound Examinations

8.1.1. Lung ultrasound examination

A complete 12-region lung ultrasound examination will be conducted with a standard ultrasound machine and a low frequency (2.5–5MhZ) convex probe. The ultrasound machine, the probe and the probe holder will be cleaned before and after each use using the dedicated antiseptic detergent indicated by hospital guidelines. The patient remains in supine position and the probe will be held perpendicular to the skin. Briefly, the 12-rib interspaces will be scanned at the bedside with the ultrasound probe applied longitudinally and perpendicularly to the exterior chest wall. The left and right hemi thorax will be assessed in six areas: two anterior areas, two lateral areas, and two posterior areas. The anterior chest will be delineated as the parasternal to the anterior axillary line and divided into upper and lower halves (zones 1 and 2). The lateral area will be delineated as the anterior to the posterior axillary line and divided into upper and basal halves (zones 3 and 4). The posterior area will be considered as the zone beyond the posterior axillary line and divided into upper and lower zones (zones 5 and 6). The lung ultrasound score (sum of patterns found on each scanning site) will be recorded (score 0: pattern with less than three Blines; score 1: Three or more separated B lines; score 2: multiple and confluent B-lines; score 3: consolidation) (36). The global lung ultrasound score will range from 0 to 36. Additional ultrasound findings include the assessment of subpleural consolidations, pleural effusions and lung sliding.

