10. STATISTICS AND ANALYSIS

For descriptive purposes continuous and ordinal variables data will be expressed as median with interquartile range. For categorical variables, percentages are calculated. Student's t-test or analysis of

variance (ANOVA) will be used to compare normally distributed numerical variables. Mann Whitney Utests and Kruskal-Wallis tests will be used to compare numerical variables when normality cannot be assumed, while chi-squared tests will be used to compare categorical variables. Univariate logistic regression analyses will be performed to identify potential factors associated with the clinical outcomes including, but not limited to, presence of interstitial syndrome, non-resolution of interstitial syndrome at 48-72h, development of ARDS and death in hospital. Multivariable logistic regression models will be used to identify independent risk factors for the same clinical outcomes. A forward and backwards stepwise approach will used to include variables into the models, with a limit of P <0.2.

Inter– observer variability of the lung ultrasound score between the study sonographer and an independent expert will be calculated on a random sample of 10 cases (120 lung regions) using Cohen K-statistics. Statistical analyses will be conducted using R (www.r-project.org). A P-value of <0.05 will be considered statistically significant. Analyses will be conducted after the end of patient recruitment and no interim analyses are planned. Statistical analysis will be performed with R software (R Foundation for Statistical Computing, Vienna, Austria).

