11.3. Data Handling and Record Keeping

The anonymized data will be stored in a secure database to guarantee the privacy of study subjects. Only local investigators will have access to the database and matching log–book. A copy of the LUS report will be attached to the patient's clinical chart to be visualized by the clinical team responsible for patient's care.

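### Nothing keeps the T2 reader from knowing the T1 score, and one overall kappa on ten single scans can neither check delta LUS nor show a directional shift

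*Combined protocol and SAP*

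**What the plan says.** Section 5 plans a 12-region lung ultrasound before delivery (T1) and a repeat afterwards (T2): "The same clinical, LUS and echocardiographic assessment will be repeated between 24 h to 72 h". Where T1 is not feasible, only the later scan is done.

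Section 4 lists two primary outcomes for resolution: "Fraction of patients with improvement or resolution of LUS findings" and "Quantitative endpoint: delta LUS score between T1 and T2".

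Sections 6.4 and 8.1.1 score each region 0 to 3. Score 1 is "Three or more separated B lines", fewer lines score 0, confluent lines score 2 and consolidation scores 3. The total runs from 0 to 36. Oedema needs at least two positive regions on each side.

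Section 11.3 attaches a copy of the ultrasound report to the "clinical chart to be visualized by the clinical team". Section 11.2 says that study data are taken from the medical chart.

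The one reader check is in section 10: inter-observer variability "between the study sonographer and an independent expert will be calculated on a random sample of 10 cases (120 lung regions"), by Cohen's kappa. The document does not mask the T2 reader to T1, and does not say whether the expert is masked to time point or to the first score.

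**The concern.** The resolution outcomes depend on visual thresholds: two lines against three, separate against confluent. A reader who knows the T1 score and the study question can shift borderline regions without intending to. The shift goes straight into delta LUS, because it acts on one of the two scans being subtracted.

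Delivery cannot be hidden from a bedside reader. The earlier score partly can, and the plan makes no attempt. The reader may meet it in two ways: the report is in the chart, and the protocol speaks of the sonographer in the singular (sections 6.3 and 10), so the same person may have done T1.

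If such a shift occurred, the estimate of resolution would be biased and the planned quality check would probably not reveal it.

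**Working it through.** **1. What the expert check covers.** Section 5 gives 2 + 2 + 2 = 6 regions per hemithorax, so 12 per scan.
- One scan per case: 10 x 1 x 12 = 120. This reproduces the plan's figure.
- Both scans per case: 10 x 2 x 12 = 240. This does not.

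If a case is a woman, no T1-T2 pair is re-read. If a case is a scan, a pair could enter by chance, but not by design.

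**2. How little it takes.** Reading 3 of 12 regions one grade lower at T2 moves delta LUS by 3 of 36 points. A woman with exactly two positive regions on one side loses the oedema criterion if one of them is read as two lines instead of three. These are illustrations; the documents do not say how often regions are misread. Losing the oedema criterion is also not the same as the categorical outcome, for which no numerical rule is given.

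**3. Kappa has no sign.** Assume expert score frequencies of 0.50, 0.25, 0.15 and 0.10 for scores 0 to 3 (not in the documents). Use kappa = (po - pe)/(1 - pe), with po the observed and pe the chance agreement.
- Under-scoring only: each region has a 25% chance of being read one grade lower, and zeros stay zero. Disagreement is 0.25 x 0.50 = 0.125, so po = 0.875. With pe = 0.366, kappa = 0.509/0.634 = 0.80. Shift per scan: -12 x 0.125 = -1.5 points.
- Error both ways: 10% down and 10% up, limited at 0 and 3. Down is 0.10 x 0.50 = 0.05 and up is 0.10 x 0.90 = 0.09, so po = 0.86. With pe = 0.3375, kappa = 0.5225/0.6625 = 0.79. Shift per scan: 12 x (0.09 - 0.05) = +0.5 points.

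Nearly equal kappas thus go with shifts of opposite sign.

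**4. Could signed differences on the same ten scans help?** The plan does not compute them. Suppose it did, with an SD of the sonographer-minus-expert difference of 2, 3 or 4 points (assumed), two-sided alpha 0.05 and the noncentral t distribution.

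| Sample | Standard error | Bias detectable at 80% power, SD 2 / 3 / 4 |
|---|---|---|
| 5 T1 scans against 5 T2 scans | SD x sqrt(1/5 + 1/5) | 4.1 / 6.1 / 8.1 (T2-specific shift) |
| All 10 scans at T2 | SD / sqrt(10) | 2.0 / 3.0 / 4.0 (T2 shift) |
| 10 T1-T2 pairs, 240 regions | SD x sqrt(2) / sqrt(10) | 2.8 / 4.2 / 5.6 (bias in delta) |
| 5 T1-T2 pairs, 120 regions | SD x sqrt(2) / sqrt(5) | 4.8 / 7.1 / 9.5 (bias in delta) |

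The pair rows assume independent reading errors at T1 and T2. With a 5/5 split, power for a 2-point shift is about 29%, 15% or 10%. With 5 pairs, power for a 3-point bias in delta is about 44%, 23% or 15%.

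**5. Direction.** The synopsis hypothesis expects incomplete resolution 48 hours after delivery. Section 4.1 expects resolution within 48 hours. The two conflict and must be reconciled. Until then, expectation bias has no fixed sign.

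**The case against.** The strongest reply is that the documents do not show any contamination. A reader might infer from section 11.3 that T2 is scored with the T1 report open. The text does not support that: it names the treating team as the readers of the chart copy and is silent on the sonographer. This stands. The supportable claim is only that nothing prevents the T2 reader from knowing T1.

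The same-reader argument also has weight. If one person does both scans, T1 is known first-hand, and withholding the chart copy masks only in part.

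A reader might also infer that the bias must run towards improvement. The opposing hypotheses rule that out.

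Fixed scoring rules and an independent expert are real, if partial, safeguards. It would therefore be too strong to say that bias is in no way limited or could never be detected: a large shift might show in signed differences if most sampled scans were T2.

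Finally, this is a single-centre, exploratory, descriptive cohort in a resource-limited hospital, where masked paired re-reading is an extra. That bears on priority. It does not answer the gap, because the main remedy needs no equipment and no second reader.

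**Conclusion.** The concern holds in a limited form. Masking of T2 to T1 is absent from the plan, and the expert check, by its own arithmetic, is ten single scans summarised by a statistic without direction. Expectation bias in delta LUS and in improvement or resolution is not limited by masking and not reliably detectable.

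The count of 120 regions is firm. The kappa comparison rests on assumed score frequencies. The detectable shifts rest on assumed SDs of 2 to 4 points and, for pairs, on independent errors. The documents give no basis for saying that bias has occurred, how large it would be or which way it would go. The point is a low-cost improvement to a primary endpoint, not a reason to doubt the design as a whole.

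**What to change.** **Main change.** Add to section 8.1.1 that all 12 T2 region scores are recorded at the bedside, on the source scan sheet, before the T1 report, T1 scan sheet or T1 CRF page is viewed. The rule must attach to the bedside record: CRF entries are transcribed from the chart, so a rule on CRF entry order would not control what was known during scoring. The cost is one sentence and, if none is in use, a scan sheet. The downside is that masking is partial when the same person did T1.

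**Optional addition.** Where clips of both scans are stored, draw the 10 women from those with both scans. The planned expert then reads T1 and T2 (240 regions) in random order, masked to time point and first score. Report signed sonographer-minus-expert differences at T1, at T2 and for delta, next to kappa. Call this a descriptive check only: in the table above, 10 pairs detect only a delta bias of about 2.8 to 5.6 points. The cost is twice the expert reading, plus clip storage and de-identification, which the document does not mention and which may be new procedures.

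**Not advised.** Do not cut the sample to 5 women to stay at 120 regions. That halves the women behind the kappa, whose regions cluster within woman, and gives a much weaker check of delta.

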6.4. Case definitions

Acute respiratory failure defined as RR≥30 breaths per minute AND/OR SpO₂/fraction of inspired oxygen (FiO₂) \leq 315 AND/OR signs of difficult breathing, including the use of accessory muscles or nasal flaring. FiO₂ will be derived from the amount of oxygen the patient receives in liters.

Clinical pulmonary oedema

Defined as respiratory distress (respiratory rate >30 breaths/min and/or SpO2 <92% on room air) with bilateral fine crepitations on chest auscultation.

Lung ultrasound consistent with pulmonary oedema (categorical)

The presence of three or more B-lines (any size and any distance apart) in a particular lung region will define a positive lung region for interstitial syndrome (30) Pulmonary edema will be defined as the presence of \geq 2 positive regions per side.

Abnormal lung ultrasound aeration score

The LUS aeration score (numerical) will be calculated: each lung field will be scored from 0 to 3 as follows: "0," A-pattern with \leq 2 B-lines; "1," more than 2 separated B-lines; "2," multiple coalescent B-lines; or "3," lung consolidation, defined as anechoic or tissue-like images arising from the pleural line that is limited in depth by an irregular border. A global LUS score will be calculated at each time point and ranged from 0 to 36.

LUS ARDS score

The three variables included in the final logistic regression model for diagnosis of ARDS are: left LUS aeration score (range 0-18), right LUS aeration score (range 0-18), and the number of antero-lateral lung regions with an abnormal pleural line (range 0-8). The LUS-ARDS score can range from 0 to 91 and is computed with the formula below. (31)

LUS-ARDS score = 2.5 x left LUS aeration score + 1 x right LUS aeration score + 3.5 x no. of anterolateral regions with an abnormal pleural line

Acute Respiratory Distress Syndrome (ARDS)

Defined according to the Berlin Definition or Kigali Modification as shown in **Table 1**.

Criteria	Berlin definition of ARDS	Kigali modification
Timing	Within 1 week of a known clinical insult, or new or worsening respiratory symptoms	
Oxygenation	PaO ₂ /FIO ₂ ≤300 mmHg SpO ₂ /FIO ₂ ≤315 mmHg	
PEEP requirement	Minimum 5 cm H ₂ O PEEP required by invasive mechanical ventilation (non-invasive acceptable for mild ARDS)	No PEEP requirement, consistent with AECC definition

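### The observer-agreement check leaves kappa weighting, unit of analysis and interval method unstated, and names no suitable agreement measure for the 0–36 score or patient-level oedema status

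*Combined protocol and SAP*

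**What the plan says.** One sentence in section 10 (Statistics and Analysis) holds the whole agreement plan. The target is the "variability of the lung ultrasound score between the study sonographer and an independent expert", assessed on a "random sample of 10 cases (120 lung regions) using Cohen K-statistics". No weighting scheme, standard error, confidence interval, target value or handling of regions within patients is given.

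Other sections define what is being scored:

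- Section 6.4: "each lung field will be scored from 0 to 3 as follows", so the region score is an ordered four-category scale. The same section classifies a patient as having oedema on ultrasound when at least two regions on each side are positive.
- Section 8.1.1: "A complete 12-region lung ultrasound examination will be conducted", so each patient contributes 12 regions. It adds that "The lung ultrasound score (sum of patterns found on each scanning site) will be recorded" and that "The global lung ultrasound score will range from 0 to 36".
- Section 4 places patient-level quantities under the primary objective: the proportion with oedema on ultrasound, "Severity endpoint: LUS aeration score (numerical 0 to 36", and "Quantitative endpoint: delta LUS score between T1 and T2".

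**The concern.** There are three gaps between what is measured and how agreement on it will be summarised.

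1. **Scale.** In its unweighted form, Cohen's kappa counts a 0 read as 1 exactly like a 0 read as 3. On an ordered scale that discards the information that matters most. The sentence does not say which form will be used, and the choice can change the result materially after the data are seen.

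2. **Unit.** The 120 regions come from 10 patients. Twelve regions share one chest and one examination, so disagreements may cluster by patient. An interval based on 120 independent units would then overstate precision.

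3. **Target.** The analysed quantities are patient-level: oedema status, the 0–36 score and its change. Agreement on single regions does not determine agreement on any of these. A reader of the results would have no measurement error for the 0–36 score against which to judge the size of a score or a change.

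**Working it through.** **The plan's own figures.** 10 cases × 12 regions = 120 regions, as stated. 12 regions × maximum 3 = 36, as stated. The plan gives no expected kappa or precision, so everything below rests on assumed inputs.

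**Weighting.** Take 120 regions with 24 disagreements (96/120 = 80% raw agreement). Let both readers assign scores 0, 1, 2, 3 to 48, 32, 24 and 16 regions.

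- Table A, all errors one step: 5 each way between 0 and 1, 4 each way between 1 and 2, 3 each way between 2 and 3; 2 × (5 + 4 + 3) = 24.
- Table B, all errors gross: 4 each way between 0 and 3, 8 each way between 0 and 2; 2 × (4 + 8) = 24.

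Unweighted kappa = (po − pe)/(1 − pe). Chance agreement is pe = (48² + 32² + 24² + 16²)/120² = 4160/14400 = 0.289. In both tables kappa = (0.80 − 0.289)/0.711 = 0.72.

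Quadratic-weighted kappa = 1 − (observed mean squared difference)/(expected mean squared difference). With identical margins the expected value is twice the variance of the score:

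- mean = (32 + 48 + 48)/120 = 1.067
- mean square = (32 + 96 + 144)/120 = 2.267
- variance = 2.267 − 1.138 = 1.129, doubled = 2.258

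Results:

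- Table A: observed 24 × 1/120 = 0.200; weighted kappa = 1 − 0.200/2.258 = 0.91.
- Table B: observed (8 × 9 + 16 × 4)/120 = 136/120 = 1.133; weighted kappa = 1 − 1.133/2.258 = 0.50.

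**Clustering.** Let rho be the within-patient correlation of disagreement, which the documents do not give. The design effect is 1 + (12 − 1) × rho, and the true standard error exceeds the independence one by its square root. Approximate coverage of a nominal 95% interval is 2Φ(1.96/ratio) − 1.

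| rho | design effect | effective regions | SE ratio | approx. coverage |
|---|---|---|---|---|
| 0 | 1.00 | 120 | 1.00 | 95% |
| 0.05 | 1.55 | 77 | 1.24 | 88% |
| 0.10 | 2.10 | 57 | 1.45 | 82% |
| 0.20 | 3.20 | 37.5 | 1.79 | 73% |
| 0.30 | 4.30 | 28 | 2.07 | 66% |

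Simulating 10 × 12 samples with patient-varying error rates (mean 20%) gives the same picture: a ratio near 1.0 without clustering, about 1.2 to 1.25 at 0.05 and up to about 2.1 at 0.30, with coverage falling from about 90% to 64%. A different model, with correlated severity and a shared reader error per patient, is milder. There the ratio is 1.02 to 1.38 for unweighted and 1.05 to 1.69 for quadratic-weighted kappa, with worst coverage 84% and 77%.

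As an interval: with po = 0.80 and pe = 0.40, kappa = 0.40/0.60 = 0.67, and the half-width is 1.96 × √(0.80 × 0.20/n)/0.60. This is 0.12 at n = 120, 0.17 at n = 57 (rho 0.10) and 0.25 at n = 28 (rho 0.30).

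**Regions versus total.** Suppose 20% of regions are off by one step. If errors go equally both ways, the mean reader difference on the 0–36 score is about 0. If all go one way, it is 12 × 0.20 × 1 = 2.4 points. Region-level agreement is 80% in both cases.

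**Precision for the total with 10 patients and 2 readers.** For an observed one-way ICC of 0.80, F = 1.80/0.20 = 9. The 97.5% F quantiles are 3.78 (9, 10 df) and 3.96 (10, 9 df), giving F limits of 9/3.78 = 2.38 and 9 × 3.96 = 35.7. Through (F − 1)/(F + 1), the 95% interval is 0.41 to 0.95. For an observed 0.90 it is 0.67 to 0.97.

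**The case against.** Several stronger readings are tempting, and the documents do not support them.

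- **That the error bars are too narrow.** The plan specifies no interval, so none exists to criticise. Clustering is not in itself a reason to reject the kappa point estimate. The point holds only if an interval is computed as though the regions were independent, which the count of 120 invites but does not state.
- **That the plan uses unweighted kappa.** Weighting is unstated, and the weighted form is also Cohen's. The defect is an open choice between materially different values.
- **That the 0–36 score is never assessed.** Section 10 names the lung ultrasound score as its target, and section 8.1.1 describes that score as a sum over sites. The count of regions makes a region-level analysis likelier, but the text is ambiguous. Neither reading rescues it: a region kappa does not determine agreement on the total, and a nominal kappa on 10 totals from a 0–36 scale would not suit.
- **That the draw should be stratified by oedema status.** At 20% prevalence a random draw of 10 has no positive patient with probability 0.8^10 = 11%. At 30% it is 0.7^10 = 2.8%, and the study's hypothesis is more than 20%. Stratifying would change the cases and the prevalence on which kappa depends, so unweighted results would no longer describe the cohort.

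It is also fair to say that the sizes are illustrative. Table B makes every error gross, which is extreme, and at low correlation the interval problem is modest. The agreement check is ancillary in an exploratory, descriptive study, and no decision threshold hangs on it. That limits the importance of the point but does not remove it: a method is named, and a better one is available on the same readings.

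**Conclusion.** The point holds in conditional form, as a cheap improvement. The documents establish an ordinal region scale, 12 regions nested in each of 10 patients, no stated weighting, unit or interval method, and no suitable agreement measure for the patient-level quantities under the primary objective.

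If kappa is unweighted, it can be 0.72 whether the weighted value is about 0.9 or about 0.5 (constructed tables, 80% raw agreement). If an interval ignores clustering, it is too narrow by about 1.2 to 2.1 times under an assumed correlation of 0.05 to 0.30. That range has no support in the documents, and other plausible models give less. The gap for the 0–36 score and oedema status depends on neither assumption.

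This is a secondary reliability check. Nothing here changes the primary frequency estimate.

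**What to change.** Amend the agreement sentence in section 10, keeping the same 10 cases and readings:

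1. State the unit of analysis. For region scores, report quadratic-weighted kappa with a confidence interval from bootstrapping patients rather than regions.
2. For the 0–36 score, report the ICC (absolute agreement) and Bland-Altman limits.
3. For patient-level oedema status, report raw agreement. At 20% prevalence only about 10 × 0.20 = 2 positive patients are expected, too few for a useful kappa.
4. Keep the simple random draw. Do not stratify by oedema status unless the results are reweighted to the cohort.
5. State that 10 patients give wide intervals, using the ICC example of 0.80 with 0.41 to 0.95.

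The cost is a sentence or two and a few lines of R, with no extra scan or reader. The downside is that the reported intervals will be visibly wide, which reflects the information that 10 patients contain.

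### Reader agreement on the lung ultrasound score is planned as Cohen's kappa over 120 regions with no weights stated; a region-level kappa does not show reader bias or the reliability of the 0 to 36 sum

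*Combined protocol and SAP*

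**What the plan says.** Section 10 (Statistics and Analysis) sets out to measure "observer variability of the lung ultrasound score between the study sonographer and an independent expert". The sample is a "random sample of 10 cases (120 lung regions" in all), and the analysis is done "using Cohen K-statistics". Nothing is said about weights, a confidence interval, or the fact that 12 regions come from each patient.

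The score being checked is defined in section 6.4: "each lung field will be scored from 0 to 3", in increasing order of aeration loss, and "A global LUS score will be calculated at each time point and ranged from 0 to 36". Section 4 uses that sum under the primary objective in two ways: "Severity endpoint: LUS aeration score (numerical 0 to 36"), and "Quantitative endpoint: delta LUS score between T1 and T2".

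No other section adds a mean reader difference, limits of agreement or an intraclass correlation (ICC) for the sum.

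**The concern.** The quantity that section 10 sets out to check and the statistic it names do not match well, for three reasons.

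- **Size.** Cohen's kappa without weights counts only exact matches. A region read as 0 by one reader and 3 by the other counts the same as 0 against 1.
- **Direction and summation.** The endpoint is a sum of 12 regions. Small one-sided differences add up in a sum, and so do differences concentrated in certain patients. A region-level kappa, weighted or not, does not report either.
- **Units.** The 120 regions come from 10 chests. If an interval is put around kappa, treating them as 120 independent observations overstates the precision.

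At stake is what the study can say about the reproducibility of a score used under its primary objective. A report of good kappa would leave open whether two readers differ by about 2 points or clearly more on the 0 to 36 scale. This is the only reliability analysis planned.

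**Working it through.** **The plan's own figures.** 10 cases x 12 regions (section 8.1.1) = 120, and 12 x 3 = 36. Both agree with the text. The plan gives no expected kappa, precision target or interval, so there is nothing further to reproduce.

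**Assumptions, none from the documents.** Region grades 0/1/2/3 occur in 70/15/10/5% of regions. The readers disagree in 10% of regions, with errors independent between regions.

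**Formulas.** Kappa = (p_o - p_e)/(1 - p_e), with p_o = 0.90. If d is the reader difference in one region, the global score difference has mean 12 E(d) and SD = sqrt(12 [E(d^2) - E(d)^2]). The half-width of the 95% limits of agreement is 1.96 SD.

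- **A. All errors one grade** (0 can only go up, 3 only down, 1 and 2 either way). E(d) = 0.10 x (0.70 - 0.05) = 0.065 and E(d^2) = 0.10. Mean 0.78, SD = sqrt(12 x 0.0958) = 1.07, half-width 2.1. Kappa = (0.90 - 0.4905)/(1 - 0.4905) = 0.80.
- **B1. All errors two or more grades**, those from 0 and 3 split evenly between two and three grades. E(d) = 0.10 x (0.70 x 2.5 + 0.15 x 2 - 0.10 x 2 - 0.05 x 2.5) = 0.1725. E(d^2) = 0.10 x (0.70 x 6.5 + 0.15 x 4 + 0.10 x 4 + 0.05 x 6.5) = 0.5875. Mean 2.1, SD = sqrt(12 x 0.5577) = 2.59, half-width 5.1. Kappa = (0.90 - 0.4876)/(1 - 0.4876) = 0.80.
- **B2. All errors as large as the scale allows.** E(d) = 0.205 and E(d^2) = 0.775. Mean 2.5, SD = sqrt(12 x 0.733) = 2.97, half-width 5.8. Kappa = (0.90 - 0.4873)/(1 - 0.4873) = 0.80.
- **Mixtures of A and B1.** With a fraction f of errors spanning two or more grades, E(d) = 0.065 + 0.1075f and E(d^2) = 0.10 + 0.4875f. For f = 0.1, 0.2 and 0.3 the half-width is 2.6, 3.0 and 3.3. Kappa stays at 0.80.
- **C. One reader one grade higher in 10% of regions, never lower.** E(d) = E(d^2) = 0.10. Mean 1.2, SD = sqrt(12 x 0.09) = 1.04, half-width 2.0, kappa 0.81.

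Quadratic-weighted kappa is 0.93 in A, 0.90, 0.87 and 0.85 in the three mixtures, 0.68 in B1, 0.60 in B2 and 0.94 in C. It responds to the size of errors but does not separate A from C.

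**Second set of assumptions.** Simulation of 200,000 patients, grades in about 50/21/18/10% of regions, 70% exact agreement:

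| Pattern of disagreement | Kappa | Weighted kappa | ICC of sum | Mean difference | Half-width |
|---|---|---|---|---|---|
| One grade, either direction | 0.57 | 0.85 | 0.94 | 1.4 | 4.6 |
| One grade, always upward | 0.58 | 0.87 | 0.90 | 3.6 | 3.3 |
| One grade upward, in about 35% of patients | 0.58 | 0.87 | 0.78 | 3.6 | 9.9 |
| Two to three grades | 0.57 | 0.26 | 0.43 | 4.5 | 13.6 |

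The second and third rows have the same weighted kappa, but their limits differ threefold.

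**Clustering.** The design effect is 1 + 11 rho, where rho is the within-patient correlation of disagreement (assumed). For rho = 0.05, 0.1 and 0.2 it is 1.55, 2.1 and 3.2. The 120 regions then carry the information of about 77, 57 and 38. An interval that treats regions as independent would be too narrow by the square root of the design effect: 1.2, 1.4 and 1.8. At rho = 0.2, simulation gave an SD of kappa of 0.109, against 0.059 for 120 independent regions, a ratio of 1.8.

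**What 10 patients can show.** For an observed one-way ICC of 0.8 with two readings, F = 1.8/0.2 = 9. The lower 95% limit is (9/3.78 - 1)/(9/3.78 + 1) = 0.41, and the upper limit is 0.95.

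**The case against.** The strongest reply is that this is a supporting quality check in a study that section 5.1 (Sample size calculation) calls explorative and descriptive. No primary estimate depends on it, and with 10 patients an ICC or limits of agreement will be wide. That stands, and it limits the weight of the point. Region-level agreement also remains relevant to the frequency endpoint, which section 6.4 builds from positive regions, although a kappa on grades 0 to 3 does not isolate that cut-point.

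Several stronger readings are tempting, but the documents do not support them.

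- **Kappa is certainly unweighted.** The text names Cohen's kappa and does not exclude weights. Unweighted is the default meaning, not a stated choice. Weights would answer only the point about size.
- **Reading error exceeds the change to be detected.** No section states a target or expected change in score. The mildest oedema-positive scan scores 4 (two regions per side at grade 1), but that is a threshold score and not a change. Limits of agreement describe single readings, not a cohort median.
- **The T1 to T2 change should be judged against the inter-reader limits.** The change is within patient, and sections 6.3 and 10 refer to the sonographer in the singular. If one person reads both visits, a constant reader bias cancels.
- **The interval will be too narrow.** Section 10 plans no interval for kappa, and clustering mainly affects precision rather than the point estimate.
- **A reading error of about 6 points is to be expected.** That figure needs every disagreement to be as large as the scale allows.

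**Conclusion.** The point holds as a minor improvement. An unqualified, region-level Cohen's kappa is a weak summary of agreement on an ordinal score that is used as a 0 to 36 sum. In its default form it ignores the size of disagreement. In any form it leaves out reader bias and the reliability of the sum.

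Under the 70/15/10/5% mix with 10% disagreement, kappa of about 0.80 is compatible with limits of agreement of plus or minus 2.1 points around the mean difference. The range is about 2.6 to 3.3 when 10 to 30% of errors span two or more grades, and 5.1 to 5.8 only as an outer bound. If an interval for kappa is reported, ignoring clustering would make it too narrow by about 1.2 to 1.8 for correlations of 0.05 to 0.2, and by more if the correlation is higher.

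The mix, error rates and correlations are all assumed, because the documents give none. The second set of assumptions leads to the same conclusion with different figures. The validity of the primary estimates is not in question.

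**What to change.** In section 10, replace the kappa sentence with three measures on the same 10 double-read cases:

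1. For region grades, quadratic-weighted kappa, with any confidence interval obtained by resampling patients rather than regions.
2. For the 0 to 36 score, the mean reader difference with limits of agreement and an ICC for absolute agreement, each with its confidence interval. This is the part that shows direction and the reliability of the sum; weighting kappa alone would not.
3. For the patient-level oedema classification, simple agreement between the two readers.

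The cost is a change of wording and slightly more analysis, with no extra scans or readers. The drawback is imprecision: the intervals from 10 patients will be wide and should be reported as such.
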